11.2 Planned Recruitment Rate

We plan to recruit 120 patients over ten months, from sites that are expected to operate on at least 1,300 eligible patients over 10 months, which equates to a maximum recruitment rate of around 11%. This should be achievable as patient-facing data collection (survey x1, phone calls x2, and interview for subset of 20 participants) is not burdensome and an RCT looking at an App to monitor surgical wounds had 69% recruitment rate.⁹

Statistical Analysis

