11.2.1 Summary of Demographic/Baseline Data and Flow of Patients

Descriptive statistics will be presented to summarize the distribution of demographic and baseline variables across each of the randomisation groups. With the exception of quality of life, which will be analysed as part of the economic analysis, the continuous baseline variables (age, height, weight, BMI) will be reported with means & 95% confidence intervals (95% CI), if shown to be normally distributed,

using a normality plot, otherwise will be reported with medians & Interquartile Ranges (IQR). The categorical and ordinal variables (gender, ethnicity, English speaker, location (urban/rural), socioeconomic status, disability, co-morbidities, smoking status, skin tone, residential status, surgical procedure, procedure type, Access to smartphone, assistance required to take photos?, given smartphone or ipad, comorbidities) will be reported with frequencies & percentages.

A Consolidated Standards of Reporting Trials (CONSORT) flow diagram will be produced, showing the frequency of patients/ participants;

- Assessed for eligibility,
- Frequency of each reason for not being eligible,
- Found eligible,
- Approached,
- Excluded before consent (and the frequency of each reason for exclusion),
- Consented,
- Excluded before randomisation (and the frequency of each reason for exclusion),
- Randomised,
- Allocated to each randomisation group,
- That received each allocated intervention,
- That did not receive each allocated intervention,
- Completed each follow up assessment (and the frequency of each reason for non-completion) for each analysis group,
- Analysed for each analysis group,
- Not analysed (and the frequency of each reason for not being analysed) for each analysis group.

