11.2.2 Primary Outcome Analysis

Safety outcomes: quality of images received, assessed by clinicians at 30 days(a quality image is one that can be used to make a clinical decision). These will be reported using frequencies and percentages.

Acceptability outcomes: clinician and patient satisfaction using surveys and interviews at day 30. The interviews will investigate the acceptability of the intervention including attitude, burden, perceived effectiveness, ethicality, intervention coherence, opportunity costs and self-efficacy and will be analysed using qualitative methods. Will also collect acceptability of being involved as a study participant. Survey variables that are continuous will be reported with means & 95% confidence intervals (95% CI), if shown to be normally distributed, using a normality plot, otherwise will be reported with medians & Interquartile Ranges (IQR). The categorical variables will be reported with frequencies & percentages.

Feasibility outcomes: recruitment rate, adherence with the module (intervention group only), loss to follow-up. Adherence will be reported as the number and percentage of adherent patients in the intervention group. To be adherent a patient needs to submit one photo with a completed questionnaire within the 30 day period. This will be compared with the progression criteria defined below. The definitive study will proceed (or not) based on these outcomes. The number and

percentage of eligible patients recruited to the study will be reported. All feasibility outcomes will be reported with 95% confidence intervals.

Progression criteria

Criteria:	Do not proceed	Proceed with changes	Proceed		
Recruitment	<10% of eligible patients	between 10% and <25% of	at least 25% of eligible		
	consent	eligible patients consent	patients consent		
Adherence with	<40% of intervention	between 40% and <80% of	at least 80% of		
the module	patients submit one or	intervention patients	intervention patients		
	more images	submit one or more images	submit one or more		
			images		
Loss to follow-up	<10% of intervention	between 10% and <60% of	at least 60% of		
	patients complete the	intervention patients	intervention patients		
	study	complete the study	complete the study		

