11.6 Analysis Groups

Recruitment rate (including access and barriers to recruitment and willingness to be randomised) will be assessed as a percentage of all eligible patients, regardless of treatment allocation. Patients who were consented but not randomised will not be included in the recruitment rate. Adherence to the module will be assessed based on patients allocated to the intervention. Loss to follow-up will be assessed based on all randomised patients..

All other patient-based analyses will be reported based on allocated treatment, except for adverse events and adverse device events, which will be reported based on the treatment the patients received.

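### Recruiting 120 of at least 1,300 eligible patients is at most 9.2%, not around 11%, so recruiting exactly to plan falls below the 10% stop line

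*Protocol*

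**What the plan says.** Section 11.2 gives the target, "We plan to recruit 120 patients over ten months", and then draws the figure at issue from the throughput of the sites, which are "expected to operate on at least 1,300 eligible patients over 10 months, which equates to a maximum recruitment rate of around 11" per cent. It calls this achievable partly because a randomised trial of a wound-monitoring app recruited 69%.

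The progression table in 11.2.2 has three bands for recruitment. *Do not proceed* applies at "<10% of eligible patients", *Proceed with changes* applies "between 10% and <25% of" eligible patients, and *Proceed* applies from 25%. All three bands are worded in terms of patients who consent. The text above the table makes the definitive study depend on these outcomes.

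Section 11.6 sets the denominator as all eligible patients and restricts the numerator: "Patients who were consented but not randomised will not be included in the recruitment rate". The CONSORT flow in 11.2.1 lists the counts that will be available, including "Found eligible", approached, consented and randomised.

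**The concern.** The planned recruitment rate and the lowest progression threshold are close together, so an error of two percentage points decides which band the plan falls in. Anyone reading 11.2 beside 11.2.2 would believe that recruiting to target clears the stop line with a small margin. If the correct rate is below 10%, one of the three criteria that govern the definitive study signals a stop when recruitment has gone as intended. The rule also cannot be applied uniquely while the table and 11.6 disagree on who is counted.

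**Working it through.** **Inputs**
- Planned recruits: 120 over ten months (11.2).
- Eligible patients over the same ten months: at least 1,300 (11.2).
- Stated rate: around 11%, described as a maximum (11.2).
- Bands: below 10%, 10% to below 25%, 25% and above (11.2.2).
- Denominator all eligible, numerator randomised (11.6).

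**Step 1: try to reproduce the stated figure.** Rate = recruited/eligible = 120/1,300 = 0.0923, or 9.2%. The stated 11% is not reproduced.
- Since 1,300 is a lower bound, larger denominators only reduce the rate: 120/1,400 = 8.6% and 120/1,500 = 8.0%.
- Solving backwards, 11% would need 120/0.11 = 1,091 eligible patients, or 0.11 × 1,300 = 143 recruits. The protocol gives neither number.
- The inverse ratio, 1,300/120 = 10.8, does come to about 11. One eligible patient in about 11 may have been written as a percentage, but this is an inference; the protocol does not show its derivation.

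**Step 2: place both figures in the table.**

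| Rate used | Band |
|---|---|
| 11% (as printed) | *Proceed with changes* |
| 9.2% (as computed) | *Do not proceed* |

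**Step 3: what each band requires.**

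| Threshold | Recruits needed from 1,300 eligible | Largest eligible pool if 120 are recruited |
|---|---|---|
| 10% | 0.10 × 1,300 = 130 | 120/0.10 = 1,200 |
| 25% | 0.25 × 1,300 = 325 | 120/0.25 = 480 |

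The planned number is 120, so with 1,300 or more eligible patients in the denominator neither threshold is met. Even the printed 11% is well short of 25%.

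**Step 4: dependence on pace.** The planned pace is 120/10 = 12 recruits per month. Assume, for illustration, that eligible patients arrive evenly at 1,300/10 = 130 per month and are counted only until the 120th recruit.
- Reaching 10% then means finishing within 1,200/130 = 9.2 months. At nine months, for instance, the rate is 120/1,170 = 10.3%.
- Reaching 25% means finishing within 480/130 = 3.7 months.

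**Step 5: dependence on the numerator.** If patients who consent are counted, as the table says, 130 consents from 1,300 give exactly 10.0%. That would need 130 − 120 = 10 patients who consented but were not randomised.

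**The case against.** The strongest reply is that 9.2% is a projection and lies close to the threshold. Three points support it.

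- The 1,300 is an expected surgical throughput. The analysis will use patients actually found eligible, with final eligibility assessed after surgery (7.1.2). Section 11.2 does not say whether its count already allows for ventilated patients, existing surgical site infection, inability to consent, or the language restriction in 7.5. A realised pool of 1,200 or fewer, about 8% lower, would lift the rate to 10%.
- The protocol does not say that eligible patients go on being counted after the 120th recruit. If counting stops then, faster uptake raises the rate. At the cited 69%, 120 recruits would come from about 120/0.69 = 174 eligible patients.
- Section 7.3.1 says that patients consented but not randomised do not count towards the sample size, so consents could exceed 120.

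These points stand as limits on the claim. A reader might infer that the cap of 120 fixes the rate whatever patients' willingness, that 25% can never be reached, or that the criterion carries no information about acceptability of recruitment. The protocol does not support those readings, which hold only at the planned pace with the full ten-month denominator. A binomial confidence interval around 9.2% would not help either side, because 120 is a planned cap and not an observed random count.

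The reply does not rescue the figure in 11.2. That section itself calls the 1,300 patients eligible, presents the number as a minimum, and divides over the same ten months. Each escape requires something other than the plan: faster accrual, a smaller pool, or ten surplus consents that 11.6 excludes anyway.

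**Conclusion.** The point holds. The rate in 11.2 should read at most 9.2%. Under 11.2.2, with the numerator and denominator of 11.6, recruiting exactly to plan returns *Do not proceed*, where the printed figure would return *Proceed with changes*. At the planned pace *Proceed* is not attainable; it would require recruitment to finish much faster than planned or a much smaller eligible pool.

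This rests on 120 randomised patients, at least 1,300 eligible patients and the full ten months in the denominator, all taken from the protocol. The shortfall against the stop line is small, 0.8 percentage points or 10 patients in 1,300, so the eventual result could fall on either side. That is not a defence of the rule: a go/no-go criterion should not signal a stop when its own plan is met. The conflict between consented and randomised patients is separate and holds whatever the rate turns out to be.

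**What to change.** 1. In 11.2, replace the stated rate with at most about 9%.
2. Use one numerator, patients randomised, in both the progression table and 11.6.
3. Make the recruitment criterion consistent with a target capped at 120, so that recruiting to plan does not trigger a stop. One option is randomised/approached; both counts are already in the CONSORT flow of 11.2.1. The 10% and 25% cut-points were written for all eligible patients, and carrying them over would loosen the rule, so they need fresh justification for the new denominator. The other option is recruits per month against the planned 12.
4. State the period over which eligible patients are counted, in particular whether counting stops at the 120th recruit.
5. Continue to report randomised/all eligible as a descriptive figure.

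The cost is a documented amendment to a progression rule; no new data are needed. Timing matters: the planned study end was 28 February 2025 and the current version is dated 19 March 2025, so the change and its reasons should be on record before the criteria are applied, and a change made after the recruitment figures are known should be declared as such. The drawback of an approached-based rate is that it does not reflect eligible patients who were never approached, which is why item 5 should be kept.

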4. TRIAL DESIGN

Two-centre, unblinded parallel-group randomised feasibility study with safety and acceptability outcomes comparing the AI module with standard care.

A total of 120 patients from will be recruited to the trial over a ten-month period. Patients will be enrolled onto the study and randomised after surgery but prior to discharge or up until day five after surgery – whichever comes first. Mixed-block 1:1 randomisation stratified by site and sex managed by Derby CTSU. Patients and staff will be aware of group allocation status.

Patients in the control group will have standard post-operative wound care follow-up. Patients in the intervention group will receive digital surgical wound monitoring with the AI module for 30 days after surgery and also standard post-operative wound care follow-up.

Standard wound follow up and the Isla digital wound monitoring platform will last for 30 days after surgery. Patients in the intervention group will be contacted via SMS text message seven days, fourteen days and twenty-one days after surgery with the link request remining open for 6 days until the next request is sent out. The exception being the last request link which will remain open until 30 days after surgery. For each request, patients are asked to submit a photo of their wound and complete the modified UKHSA wound surveillance questionnaire.⁵

At consent will collect baseline quality of life data (SF-6Dv2)

After 30 days we will collect the following data:

- online satisfaction and quality of life survey with participants in both groups
- online satisfaction survey with staff
- interviews (focusing on satisfaction and experience) with a subsection of 10 patients from both groups – 20 in total
- interviews (focusing on satisfaction and experience) with a subsection of 10 staff
- •
- Phone call to all patients to discuss their wound and any treatments or healthcare interventions / engagement they may have had. (

After 60 days we will collect the following data:

- Medical case note review for all patients to identify re-admissions or further surgery
- Patient phone call to discuss their wound and any treatments or healthcare interventions / engagement they may have had and quality of life.

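### Recruiting exactly to plan gives at most 9.2% of eligible patients, not around 11%, which on the section 11.6 definition falls in the plan's own 'Do not proceed' band

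*Protocol*

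**What the plan says.** Three parts of the protocol bear on the recruitment rate.

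- **Plan (section 11.2; section 4 gives the same target and period).** "We plan to recruit 120 patients over ten months", from sites "expected to operate on at least 1,300 eligible patients over 10 months, which equates to a maximum recruitment rate of around 11" per cent.
- **Progression criteria (section 11.2.2, recruitment row).** 'Do not proceed' applies when "<10% of eligible patients" consent, 'Proceed with changes' from 10% to below 25%, and 'Proceed' when "at least 25% of eligible" patients consent. The section makes the decision on a definitive study depend on the feasibility outcomes in this table.
- **Definition of the rate (section 11.6).** Recruitment "will be assessed as a percentage of all eligible patients, regardless of treatment allocation". Patients who consent but are not randomised are left out of the rate.

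**The concern.** The stated percentage does not follow from the two counts beside it, and the error straddles a decision boundary. At 11% the plan appears to sit just above the lowest cut-point; at the rate the counts give, it sits below. Recruitment is one of only three progression criteria and a primary feasibility outcome.

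There is also a structural problem. The numerator is limited to a target of 120, while the denominator is every eligible patient operated on while recruitment is open. On the stated schedule the rate therefore mostly reflects the size of the target relative to the sites' throughput, and says little about whether patients are willing to join. A trial that met its target on time could receive an unfavourable reading for a reason unrelated to feasibility, and the sponsor would then have to explain that reading with the results in hand.

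**Working it through.** **Inputs.** Target 120 over 10 months, i.e. 12 a month (sections 4 and 11.2). Eligible patients at least 1,300 over the same 10 months, i.e. at least 130 a month (11.2). Stated rate around 11% (11.2). Cut-points 10% and 25% (11.2.2). Denominator all eligible patients, numerator randomised patients (11.6).

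**1. Attempt to reproduce the stated figure.** Rate = recruited / eligible = 120 / 1,300 = 9.2%. The monthly form, 12 / 130, gives the same. More eligible patients only lower it: 120 / 1,400 = 8.6% and 120 / 1,500 = 8.0%. So 9.2% is the maximum, and the 11% is not reproduced.

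**2. What would give 11%?**
- More recruits: 0.11 × 1,300 = 143, against a target of 120.
- Fewer eligible patients: 120 / 0.11 = 1,091. Allowing for rounding, 10.5% to 11.5% corresponds to about 1,143 down to 1,043. None of these is close to 1,300.
- 1,300 as a 12-month figure: 1,300 × 10/12 = 1,083, and 120 / 1,083 = 11.1%. This matches, but it is an assumption that contradicts the printed ten months.

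**3. Position against the cut-points, with 1,300 eligible.**

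| Band boundary | Recruits needed from 1,300 | Most eligible patients if recruits = 120 | Time at 130 a month |
|---|---|---|---|
| 10% | 0.10 × 1,300 = 130 | 120 / 0.10 = 1,200 | 1,200 / 130 = 9.2 months |
| 25% | 0.25 × 1,300 = 325 | 120 / 0.25 = 480 | 480 / 130 = 3.7 months |

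The planned 120 is 10 short of the lower boundary. The upper boundary is 325 / 120 = 2.7 times the target.

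**4. The same check if 1,300 is annual (assumption).** The planned rate of 11.1% falls in 'Proceed with changes'. 'Proceed' would need 0.25 × 1,083 = 271 recruits, or 120 within 480 / 108.3 = 4.4 months. It stays out of reach on the ten-month schedule.

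**5. Effect of the numerator.** If the table's wording (consent) governs and 120 are randomised, 10 further patients who consented but were not randomised would give 130 / 1,300 = 10.0%, which is 'Proceed with changes'. Under 11.6 the same trial scores 9.2%. The two sections can therefore put one trial in two bands.

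**The case against.** A reader might infer that the criterion is bound to fail and that the sponsor would have to abandon the definitive study after a fully recruited trial. The documents do not support that, for three reasons.

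- **The denominator is a forecast.** The observed count will come from the CONSORT flow in 11.2.1. Final eligibility is assessed after surgery (7.1.2), and patients who cannot consent (7.2), or who have neither English nor a translating carer (7.5), are not recruited. The protocol does not say whether 1,300 already allows for them. An observed count of 1,200 or fewer, a shortfall of 100 / 1,300 = 7.7%, would bring 120 recruits to 10%. Finishing in about 9.2 months at the forecast throughput would do the same.
- **The numerator is unsettled.** Section 7.3.1 foresees patients who consent but are not randomised, and they do not count towards the 120. Under the table's wording they could lift the rate to the boundary.
- **No rule makes one criterion decisive.** Section 11.2.2 ties the decision to the outcomes together and does not state that a single result in the lowest band stops the definitive study.

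It is also fair to say that the 1,300 rather than the 11% may be the misprint.

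These points limit the claim but do not remove it. The printed figures still disagree, the plan as printed sits below the lowest cut-point on the 11.6 definition, and neither candidate correction brings 'Proceed' within reach on schedule.

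**Conclusion.** The point holds as an internal inconsistency that should be corrected. On the printed figures the planned rate is at most 9.2%, about two percentage points below the stated 11% and on the other side of the 10% cut-point. That placement rests on three things: 1,300 or more eligible patients over ten months, exactly 120 recruits over that period, and the 11.6 numerator. If 1,300 turns out to be annual, the planned rate is 11.1% and the band becomes 'Proceed with changes'.

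The finding about the top band is the more robust one: 'Proceed' is incompatible with taking ten months to recruit 120 under either reading. The finding concerns the plan and its decision rule; it does not predict the trial's result and does not affect the analysis of the other outcomes.

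**What to change.** 1. **Reconcile section 11.2.** Check the source of the 1,300. If it stands for ten months, state the planned rate as at most about 9.2%. If it is an annual figure, correct the count or the period.
2. **Use one numerator.** State in both 11.2.2 and 11.6 whether the criterion counts patients who consent or patients who are randomised.
3. **Make the criterion compatible with a fixed target of 120**, by one of two routes:
   - base it on eligible patients approached, which the CONSORT flow in 11.2.1 already counts, and report recruitment pace against 12 a month beside it. The 10% and 25% cut-points were set for all eligible patients and should not be carried over; they need fresh justification, and the approach process should be described because selective approaching can raise this rate; or
   - keep all eligible patients as the denominator and reset both cut-points relative to the planned rate.
4. **Date the change** before the progression results are read. Version 2.2 is dated 19 March 2025, after the planned study end of 28 February 2025, so recruitment counts may already be known. In that case, report the rate on both denominators and disclose when and why the criterion changed.

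**Cost.** The change is to wording and needs no new data. It does need the sponsor's classification as substantial or non-substantial and the matching approval or acknowledgement under section 13.8. If made late, the revised criterion will carry less weight than one fixed in advance.

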11.2.1 Summary of Demographic/Baseline Data and Flow of Patients

Descriptive statistics will be presented to summarize the distribution of demographic and baseline variables across each of the randomisation groups. With the exception of quality of life, which will be analysed as part of the economic analysis, the continuous baseline variables (age, height, weight, BMI) will be reported with means & 95% confidence intervals (95% CI), if shown to be normally distributed,

using a normality plot, otherwise will be reported with medians & Interquartile Ranges (IQR). The categorical and ordinal variables (gender, ethnicity, English speaker, location (urban/rural), socioeconomic status, disability, co-morbidities, smoking status, skin tone, residential status, surgical procedure, procedure type, Access to smartphone, assistance required to take photos?, given smartphone or ipad, comorbidities) will be reported with frequencies & percentages.

A Consolidated Standards of Reporting Trials (CONSORT) flow diagram will be produced, showing the frequency of patients/ participants;

- Assessed for eligibility,
- Frequency of each reason for not being eligible,
- Found eligible,
- Approached,
- Excluded before consent (and the frequency of each reason for exclusion),
- Consented,
- Excluded before randomisation (and the frequency of each reason for exclusion),
- Randomised,
- Allocated to each randomisation group,
- That received each allocated intervention,
- That did not receive each allocated intervention,
- Completed each follow up assessment (and the frequency of each reason for non-completion) for each analysis group,
- Analysed for each analysis group,
- Not analysed (and the frequency of each reason for not being analysed) for each analysis group.

